6.4.8. Concomitant Medication Review

A review of concomitant medications will be conducted at V1 and at every trial visit. Any medications taken by trial patients will be recorded in source documents and on the appropriate CRF.

6.4.11. Clinical Laboratory Tests

Clinical safety laboratory tests are to be performed by the local laboratory until central laboratory services become available. Patients are to be fasting for at least 8 hours and labs are to be drawn prior to dosing, but after measurement of vital signs.

All clinically significant laboratory abnormalities will be followed-up by repeat testing and further investigated according to the judgment of the investigator.

In certain situations, it may not be feasible to complete all blood draws scheduled for a specific visit (e.g., a younger patient, or difficulty with phlebotomy). In this situation, the investigator may use his/her discretion to determine which laboratory tests are completed. Laboratory tests should be prioritized in the following manner:

- 1. safety laboratory tests,
- 2. anti-drug antibodies (ADA),
- 3.
- 4. glycated hemoglobin (HbA1c),
- 5.

 6.
- 7. laboratory assessments indicative of nutritional status (e.g., albumin).

Any patient who does not complete all blood draws as described in the SOA (Table 1) on 2 consecutive visits should be discussed with the sponsor.

Specific tests are described below.

6.4.11.1. Hematology, Clinical Chemistry and Urinalysis

Hematology:

Complete blood count with platelet count and standard indices will be obtained.

Chemistry:

Sodium, potassium, chloride, CO₂, albumin, total protein, glucose, blood urea nitrogen (BUN), creatinine, uric acid, AST, ALT, gamma-glutamyltranspeptidase (GGT), creatine phosphokinase (CPK), alkaline phosphatase, total bilirubin, direct bilirubin, lactate dehydrogenase (LDH), calcium, and phosphorus will be obtained.

and HbA1c

HbA1c will also be collected. Blood samples will need to be collected when the patient is in the fasted state.

[figure not shown]
Urinalysis:

pH, glucose, protein, ketones, bilirubin, blood, urobilinogen, specific gravity, nitrite, and leukocytes by dipstick analysis or machine urinalysis will be measured. Urine microscopic examination will be performed if positive findings on dipsticks warrant further examination.

6.4.12.

6.4.13. Pediatric Nutritional Assay

For pediatric patients (age 2 to 11 years) only, Nutritional Counseling and Monitoring may be performed by a qualified dietician or nutritionist (or equivalent) to ensure that pediatric patients have adequate nutritional/dietary intake to maintain proper growth and development. Additional laboratory assessments indicative of nutritional status may be performed, at the investigator's discretion, in case of rapid and conspicuous weight loss (e.g., albumin) (Bharadwaj 2016). In this occurrence, the investigator should inform the sponsor who may request additional assessments.

6.4.15. Injection Site Evaluation and Scoring

Injection sites will be carefully inspected, evaluated and scored during the trial period. The injection site evaluation will include identification and measurement of areas of erythema,

edema, and induration, as well as the presence of localized pain, tenderness and itching. A sample injection site evaluation form is included in Appendix 11.1.

In addition, unscheduled evaluations may also be recorded as warranted by clinical conditions, including in the interval between scheduled visits.

6.4.16. Anti-Setmelanotide Antibody (ADA) Measurements

Blood samples for measurement of anti-setmelanotide antibodies will be collected at each visit. Any patient with a positive titer will be followed \sim every 3 months after detection until resolution or return to baseline.

6.4.17.

RM-493-022 V8.1

Protocol

6.4.17.3.

6.4.18. Diet and Nutritional Counseling

For adolescent and adult patients, no special dietary counseling will be part of this trial, but patients will be counseled to adhere to a calorie reduced diet, at the discretion of the investigator.

For pediatric patients (age 2-11 years), nutritional counseling and monitoring may be performed by a qualified dietician or nutritionist (or equivalent), at the investigator's discretion, according to the SOA (Table 1), to ensure that pediatric patients have adequate nutritional/dietary intake to maintain proper growth and development. Additional laboratory assessments indicative of nutritional status may be monitored as appropriate (e.g., albumin).

6.4.19. Adverse Events

Each patient must be carefully monitored for the development of any AEs throughout the trial from V1 through the patient's last visit. This information should be obtained in the form of non-leading questions (e.g., "How are you feeling?"), and from signs and symptoms detected during each examination, from laboratory evaluation, observations of trial personnel, and spontaneous reports from patients.

All AEs, including injection site reactions and potential systemic reactions will be graded using the National Cancer Institute Common Terminology Criteria for Adverse Events (CTCAE) grading system.

Complete details on AE monitoring are provided in Section 7.

6.4.20. Order of Assessments

When scheduled at the same timepoint, the order of procedures should be as follows: obtain vital signs, perform 12-lead ECG, followed by blood draws (at the specified time point, if applicable). Adjustments may be made depending upon specific circumstances. Questionnaires are to be completed before the morning meal and study drug administration; they may be performed before or after blood draws and/or 12-lead ECGs.

7. ADVERSE EVENTS

Monitoring of adverse events (AEs) will be conducted throughout the trial. AEs will be recorded in the CRFs from V1 through the patient's last visit, as indicated in Table 1. AEs that occur after the start of study drug administration will be considered treatment-emergent adverse events. Any AEs that are reported as ongoing at the time of the subject's final visit in their index trial, will be recorded as pre-existing condition on the trial AE logs. Serious adverse events (SAEs) will be recorded through the patient's last visit. All AEs should be monitored until they are resolved or are clearly determined to be due to a patient's stable or chronic condition or intercurrent illness(es).

7.1. Definitions, Documentation, and Reporting

An AE is any untoward medical occurrence associated with the use of a drug in humans, whether or not considered drug related. An AE (also referred to as an adverse experience) can be any unfavorable and unintended sign (e.g., an abnormal laboratory finding), symptom, or disease temporally associated with the use of a drug, without any judgment about causality. An AE can

arise from any use of the drug (e.g., off-label use, use in combination with another drug) and from any route of administration, formulation, or dose, including an overdose.

An AE or suspected adverse reaction is considered serious (SAE) if, in the view of either the investigator or sponsor, it results in any of the following outcomes:

- Death.
- Life-threatening. Life-threatening means that the patient was at immediate risk of death from the reaction as it occurred, i.e., it does not include a reaction, which hypothetically might have caused death had it occurred in a more severe form.
- In-patient hospitalization or prolongation of existing hospitalization. Hospitalization admissions and/or surgical operations scheduled to occur during the trial period, but planned prior to trial entry are not considered AEs if the illness or disease existed before the patient was enrolled in the trial, provided that it did not deteriorate in an unexpected manner during the trial (e.g., surgery performed earlier than planned).
- A persistent or significant incapacity or substantial disruption of the ability to conduct normal life functions.
- Congenital anomaly/birth defect.
- Important medical event. An important medical event is an event that may not result in death, be life-threatening, or require hospitalization but may be considered an SAE when, based upon appropriate medical judgment, it may jeopardize the patient or patient and may require medical or surgical intervention to prevent one of the outcomes listed in the definitions for SAEs. Examples of such medical events include allergic bronchospasm requiring intensive treatment in an emergency room or at home, blood dyscrasias or convulsions that do not result in in-patient hospitalization, or the development of drug dependency or drug abuse.

7.2. Procedures for AE and SAE Reporting

Each patient must be carefully monitored for the development of any AEs. This information should be obtained in the form of non-leading questions (e.g., "How are you feeling?") and from signs and symptoms detected during each examination, observations of trial personnel, and spontaneous reports from patients.

All AEs (serious and non-serious) spontaneously reported by the patient and/or in response to an open question from trial personnel or revealed by observation, physical examination or other diagnostic procedures will be recorded on the appropriate CRF. Any clinically relevant deterioration in laboratory assessments or other clinical findings is considered an AE and must be recorded on the appropriate CRF. When possible, signs and symptoms indicating a common underlying pathology should be noted as 1 comprehensive event.

All SAEs that occur during the course of the trial must be reported by the investigator to the sponsor or designee **within 24 hours** from the point in time when the investigator becomes aware of the SAE. All SAEs must be reported whether or not considered causally related to the study drug. An SAE Report Form will be completed and sent to the sponsor within 24 hours. The information collected will include patient number, a narrative description of the event, and an

assessment by the investigator as to the severity of the event and relatedness to study drug. All SAEs must also be entered into the CRFs. Follow-up information on the SAE may be requested by the sponsor or its designee.

Sites will submit all SAE Report Forms within 24 hours via email or fax to the address below:

If there are serious, unexpected adverse drug reactions associated with the use of the study drug, the sponsor or designee will notify the appropriate regulatory agency/agencies and all participating investigators on an expedited basis. It is the responsibility of the investigator to promptly notify the IRB/IEC where required of the IRB/IEC of all unexpected serious adverse drug reactions involving risk to human patients.

7.2.1. Assessment of Severity, Relationship to Study Drug, and Expectedness

For both serious and non-serious AEs, the investigator must determine both the severity of the event and the relationship of the event to study drug administration. Only those injection site reactions and laboratory abnormalities considered clinically significant by the investigator will be recorded as AEs. Expectedness will be evaluated by the sponsor.

7.2.1.1. Assessment of Severity

Intensity of AEs including clinically significant treatment-emergent laboratory abnormalities, injection site reactions and potential systemic reactions will be graded according to the CTCAE Version 4.0. The CTCAE grade refers to the severity of the AE and ranges from Grade 1 (mild AE), Grade 2 (moderate AE), Grade 3 (severe AE), and Grade 4 (life-threatening or disabling AE) to Grade 5 (death related to AE).

Adverse events not listed by the CTCAE, including hyperpigmentation, will be graded as follows:

- Mild: discomfort noticed but no disruption of normal daily activity.
- Moderate: discomfort sufficient to reduce or affect daily activity.
- Severe: inability to work or perform normal daily activity.
- Life threatening: represents an immediate threat to life.

7.2.1.2. Assessment of Relationship

Relationship to of an AE to study drug administration will be determined by the investigator according to the following criteria:

- None: No relationship between the event and the administration of study drug. The event is related to other etiologies, such as concomitant medications or patient's clinical state.
- Unlikely: The current state of knowledge indicates that a relationship to study drug is unlikely or the temporal relationship is such that study drug would not have had any reasonable association with the observed event.

- **Possible:** A reaction that follows a plausible temporal sequence from administration of the study drug and follows a known response pattern to the suspected study drug. The reaction might have been produced by the patient's clinical state or other modes of therapy administered to the patient.
- **Probable:** A reaction that follows a plausible temporal sequence from administration of the study drug and follows a known response pattern to the suspected study drug. The reaction cannot be reasonably explained by the known characteristics of the patient's clinical state or other modes of therapy administered to the patient.

For the purpose of safety analyses, all AEs that are classified as possible or probable will be considered treatment-related events.

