7.2.1.3. Assessment of Expectedness

The reference safety information (RSI) for this trial will be within the current IB. The sponsor will be responsible for assessment of expectedness for all AEs to determine regulatory reporting requirements. An unexpected AE is one that is not listed within the RSI of the IB.

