8.4. Statistical Methods

Statistical methods, populations and approaches to missing data will be outlined in the SAP.

As these patient populations are extremely rare, efforts will be made to keep all patients in the trial, and all data collected, even if outside of visit windows, will be included in all analyses of endpoints. No missing data will be imputed, analyses will be carried out on all available data.

With respect to the exploratory endpoints, no adjustment for multiplicity will be included for the many patient populations in this trial as these different populations are included in this trial only for administrative convenience.

AEs will be coded by using the most current version of Medical Dictionary for Regulatory Activities (MedDRA) and summarized by system organ class and preferred term for the number and percent of AEs reported, the number of patients reporting each AE, and the number of patients with any AE.

Analyses of AEs will be performed for those events that are considered treatment-emergent, where treatment-emergent is defined as any AE with onset after the administration of study drug through the end of the trial, specifically, 30 days after the last dose of setmelanotide, or any event that was present at baseline but worsened in severity or was subsequently considered drug-related by the investigator through the end of the trial.

A by-patient AE data listing including onset and resolution dates, verbatim term, preferred term, treatment, severity, relationship to treatment, action taken, and outcome will be provided.

Safety data including laboratory evaluations and vital signs assessments will be summarized by time of collection. In addition, change from baseline to any post-dose values will be summarized for vital signs and clinical laboratory results. Frequency of patients with abnormal safety laboratory results will be tabulated.

Safety and efficacy data from both the index and extension trial may be combined to evaluate long-term safety and efficacy outcomes on a patient specific and population basis.

It is planned that analyses may be completed once all patients within each sub-population/cohort have completed at least 1 year of this extension protocol, data have been cleaned and finalized, and the database is locked for assessments in this first year. Additional supplemental analyses will be conducted on a yearly basis for patients who continue in the trial (for up to 7 years).

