3.11. Missing, Unused, and Spurious Data

In general, no missing data will be imputed for this extension study and analyses will be carried out on all available data. Imputation of missing questionnaire data will be applied for the derivation of summary scores, dependent on the questionnaire and imputation rules of the questionnaire. Questionnaire-specific imputation rules will be outlined in the sections below, as applicable.

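### Both categories counted as treatment-related require a known response pattern, so on the written criteria a new type of reaction is not counted as related

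*Protocol*

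**What the plan says.** Protocol 7.2.1.2 gives the investigator four relationship categories. Possible and Probable open with the same requirement, that the reaction "follows a plausible temporal sequence from administration of the study drug and follows a known response pattern to the suspected study drug". They differ only on whether the patient's condition or another therapy could explain the event. The counting rule is that "all AEs that are classified as possible or probable will be considered treatment-related events".

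Expectedness is a separate step, assigned to the sponsor in Protocol 7.2.1.3: "An unexpected AE is one that is not listed within the RSI of the IB". Protocol 7.2 provides for expedited notification of "serious, unexpected adverse drug reactions associated with the use of the study drug".

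The rating is used in two places in the analysis:

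- SAP 4.5.2 makes drug-related AEs a focus of the AE summary and asks for by-subject listings of drug-related AEs and drug-related SAEs. The legible SAP does not redefine relatedness.
- Protocol 7 says that AEs still ongoing at a patient's "final visit in their index trial, will be recorded as pre-existing condition on the trial AE logs". Protocol 8.4 then admits such an event to the treatment-emergent set only if it was "present at baseline but worsened in severity or was subsequently considered drug-related by the investigator".

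**The concern.** The primary objective is long-term safety, in an open-label, single-arm trial with treatment for up to 7 years. Such a trial should be able to show a reaction not seen before. The relatedness criteria work against that, because they make prior familiarity a condition of being counted. An investigator who finds no other explanation for a new event, and who follows the criteria to the letter, cannot rate it Possible or Probable.

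The drug-related AE summary and listings would then leave out the type of event for which they are most useful. With no control arm, there is no comparison rate to reveal an excess by another route.

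**Working it through.** No figure in the plan can be recomputed here. The check applies the definitions to a test case and then traces where the rating is used.

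**Step 1: the test case.** Take an AE with plausible timing, no other cause, no known pattern, and no existing knowledge that points against the drug.

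| Category | Requires | Met? | Counted as related? |
|---|---|---|---|
| None | Another etiology | No | No |
| Unlikely | Knowledge indicating that a relationship is unlikely, or implausible timing | No on a strict reading; the first limb could be stretched | No |
| Possible | Plausible timing and known pattern; another cause might explain it | No, pattern missing | Yes |
| Probable | Plausible timing and known pattern; no other reasonable explanation | No, pattern missing | Yes |

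**Step 2: all combinations.** Four yes/no attributes (plausible timing, known pattern, other cause, current knowledge indicating unlikely) give 2 × 2 × 2 × 2 = 16 profiles.

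- Timing plausible and pattern known: 4 profiles. All meet Possible or Probable.
- Timing implausible and pattern known: 4 profiles. None is counted.
- No known pattern: 8 profiles. None is counted, whatever the other three attributes. Four of them have implausible timing and fall under Unlikely. Two have plausible timing and another cause and can be placed in None. One has plausible timing, no other cause and knowledge against a relationship, and falls under Unlikely. The last is the test case, the only one of the 16 that meets no definition.

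If a site places the test case in Unlikely by default, it is still not counted, so the result does not depend on how strictly Unlikely is read.

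**Step 3: the outputs affected.** The listing sentence in SAP 4.5.2 has six entries: drug-related AEs, treatment-emergent SAEs, drug-related SAEs, deaths, AEs leading to withdrawal, and subject deaths. Deaths appear twice, so five are distinct. Two of the five (40%) are filtered on relatedness. A non-serious AE that does not lead to withdrawal and is not rated related is in none of the five. The summary sentence just before breaks off in the public text, and nothing is inferred from that.

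**Step 4: treatment-emergent status.** Protocol 8.4 gives three routes: onset after study drug, present at baseline and worsened, and present at baseline and later considered drug-related. Only the third uses the rating. It decides the matter only for an AE carried over from the index trial that does not worsen.

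**Step 5: what the rating does not touch.** SAP 4.5.2 says that all AEs are displayed in tables and listings by SOC and PT. Protocol 8.4 promises a by-patient AE listing that shows the relationship. For serious events in the trial, "All SAEs must be reported whether or not considered causally related to the study drug". The laboratory, vital-sign, ECG, examination and injection-site summaries do not use the rating.

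**The case against.** The strongest reply is that the rating is a clinical judgement and that nothing is hidden. The term known response pattern is undefined and not tied to the RSI, so an investigator may accept a pharmacologically coherent event as fitting one. The event and its rating remain in the by-patient listing, where any reader can re-cut the data. The proposed wider set also takes in events rated Unlikely for implausible timing, which are not the problem. All of this stands and limits the severity. It does not remove the fault: loose reading means departing from the written criteria, and different sites may depart from them differently.

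A reader might go further than the documents allow in four ways.

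- **A contradiction with the expectedness rules.** Being unlisted in the RSI is not the same as having no known pattern, and an event can fit a pattern and still be unlisted. The sections are in tension but can stand together.
- **Many blank ratings that drop out.** SAP 3.11 does say "In general, no missing data will be imputed for this extension study", and the legible SAP has no rule for a missing relationship. But Protocol 7.2.1 obliges the investigator to determine the relationship for every AE, Protocol 9.7.5 sends missing data to sites as queries, and Protocol 9.7.1 ties eCRF completeness to resolving them. Blanks should be rare; Unlikely by default is the likelier path.
- **New events lost from the treatment-emergent set.** An event with onset after study drug enters by the first route whatever its rating.
- **Post-trial SAEs going unreported.** Protocol 7.4 asks only what the investigator considers related, while the counting rule in 7.2.1.2 is stated for safety analyses. An effect there is speculation.

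**Conclusion.** The point holds as a minor one. Both counted categories (2 of 2) require a known pattern, so on the written criteria a new type of reaction with plausible timing and no other cause is not counted as related, whether it is left without a clean category or placed in Unlikely.

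The effect is confined to the drug-related AE summary, the drug-related AE and SAE listings, and the treatment-emergent status of carried-over AEs that do not worsen. The conclusion assumes that investigators apply the criteria as written and that no redacted SAP text redefines relatedness.

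The number of AEs affected cannot be computed, because the documents give no AE counts. SAP Table 1-1 shows 9 + 13 + 119 + 12 + 38 + 14 + 1 = 206 subjects from index trials, any of whom could carry over an AE. That is a headcount and should not be read as the size of the problem.

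**What to change.** 1. **SAP 4.5.2.** Keep the primary definition. Add one sensitivity summary by SOC and PT and one by-subject listing in which related means every AE not rated None, that is Unlikely, Possible and Probable. Count as related any rating still missing after queries. In the listing, flag carried-over AEs that become treatment-emergent only under this wider definition. The cost is one table and one listing from a field already collected. The downside is that the wider set includes more background events, among them those rated Unlikely for implausible timing, and so gives higher related percentages. The primary summary is unchanged.

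2. **Protocol 7.2.1.2, at the next amendment.** Make the known response pattern supportive rather than required for Possible, and leave known versus unknown to the expectedness step in 7.2.1.3. Flag each AE by the definition in force when it was rated, so that two definitions are not mixed unmarked in one table. Under Protocol 9.5 this needs written IRB/IEC approval and submission to regulators, and sites must be told. It affects only later ratings, so it need not prompt an amendment of its own.
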